4.5.6 Patient-Reported and Clinician-Reported Outcomes Assessed during Site Visits

Patients will complete patient-reported outcome (PRO) assessments to capture their direct experience and potentially characterize the clinical impact of MSTT1041A. The questionnaires, translated into the local language as required, will be completed in their entirety at specified timepoints during the study. To ensure instrument validity and that data standards meet health authority requirements, questionnaires will be self-administered before the patient receives any information on disease status, prior to the performance of other site-visit assessments and procedures and prior to the administration of study treatment.

Clinician-reported outcome (ClinRO) data will be collected via a self-administered questionnaire to allow clinicians to report their impression of each patient's change in asthma symptoms. Clinicians will complete the questionnaire after they have examined patients and performed other study-related health assessments.

Patients will use an electronic device to complete their PRO assessments. The PRO questionnaires will be pre-programmed on electronic devices so that the appropriate questionnaires will be administered in order at specific site visits as specified in the schedule of activities (see [Appendix 1](#)). The PRO assessments should take between approximately 5 and 25 minutes to complete (shorter at most visits, longer at the randomization visit, Week 26, and Week 54 visit). The electronic device and/or instructions for completing the questionnaires electronically will be provided by the investigator staff. The data will be transmitted to a centralized database maintained by the electronic device vendor. The data will be available for access by appropriate study personnel.

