4.5.13 Fractional Exhaled Nitric Oxide

FeNO is a volatile marker of airway inflammation and has been demonstrated to decrease with ICS treatment. Standard nitric oxide machines will be provided to the site and should be used for all study-related FeNO measurements. Patients will be asked to refrain from nitrate-rich foods (such as processed meats [bacon, lunchmeat, hot dogs, sausage], spinach, green beans, broccoli, and cauliflower) for at least 8 hours prior to the study visit and to avoid food or drink for at least 1 hour prior to completing at least three (and up to six) separate measurements according to ATS guidelines (training and guidance to be provided separately) (American Thoracic Society 2005).

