5.3.5.5 Abnormal Laboratory Values

Not every laboratory abnormality qualifies as an adverse event. A laboratory test result must be reported as an adverse event if it meets any of the following criteria:

- Is accompanied by clinical symptoms
- Results in a change in study treatment (e.g., treatment interruption or treatment discontinuation)
- Results in a medical intervention (e.g., potassium supplementation for hypokalemia) or a change in concomitant therapy
- Is clinically significant in the investigator's judgment

It is the investigator's responsibility to review all laboratory findings. Medical and scientific judgment should be exercised in deciding whether an isolated laboratory abnormality should be classified as an adverse event.

If a clinically significant laboratory abnormality is a sign of a disease or syndrome (e.g., alkaline phosphatase and bilirubin $5 \times$ ULN associated with cholestasis), only the diagnosis (i.e., cholestasis) should be recorded on the Adverse Event eCRF.

If a clinically significant laboratory abnormality is not a sign of a disease or syndrome, the abnormality itself should be recorded on the Adverse Event eCRF, along with a descriptor indicating whether the test result is above or below the normal range (e.g., "elevated potassium," as opposed to "abnormal potassium"). If the laboratory abnormality can be characterized by a precise clinical term per standard definitions, the clinical term should be recorded as the adverse event. For example, an elevated serum potassium level of 7.0 mEq/L should be recorded as "hyperkalemia."

Observations of the same clinically significant laboratory abnormality from visit to visit should only be recorded once on the Adverse Event eCRF (see Section 5.3.5.4 for details on recording persistent adverse events).

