6.8 BIOMARKER ANALYSES

Potential predictive biomarkers of MSTT1041A response will be assessed in primary and key secondary endpoints (e.g., asthma exacerbation rate, FEV₁) to assess if a subset of patients derives enhanced clinical benefit from MSTT1041A. Predictive biomarker candidates include, but are not limited to, blood eosinophils, and germline mutations in *IL1RL1*.

PD biomarkers (e.g., FeNO) will be assessed to determine pharmacological activity and mechanism of action of MSTT1041A in patients with asthma. Data will be summarized by absolute levels of the biomarker, as well as absolute and relative changes from levels at the randomization visit, for each treatment group. Additional PD analyses will be conducted as appropriate.

Further details related to biomarker analyses will be described in the SAP.

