^f Atopy status (atopic or non-atopic) will be assessed on the basis of historical documentation (e.g., patient's medical records), as described in Section 4.5.4.

^g PRO questionnaires will be completed before the patient receives any information on disease status, prior to the performance of other site-visit assessments and procedures, and prior to the administration of study treatment. Both the full (7 items) and 5 item (ACQ-5) version of the ACQ will be administered in this study. The ACQ-5 is part of the eligibility criteria and will be administered at screening and run-in visits. The full ACQ-7 will be administered at the remaining timepoints as indicated in the Schedule of Activities (randomization visit, Week 26, and Week 54).

^h Clinicians will complete the CGIC after they have examined the patient and evaluated data that support an overall health assessment, which may include, but are not limited to, FEV₁, FeNO, and medical records.

ⁱ Includes evaluation of the head, eyes, ears, nose, and throat, and the cardiovascular, dermatological, musculoskeletal, respiratory, gastrointestinal, and neurological systems. Record abnormalities observed prior to dosing at Visit 2 on the General Medical History and Baseline Conditions eCRF. At subsequent visits, record new or worsened clinically significant abnormalities on the Adverse Event eCRF.

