Appendix 8 Clinician Global Impression of Change

Clinician Global Impression of Change (CGIC)

How would you rate the change in the subject's asthma symptoms since they started taking the study drug?

- Very much improved
- Much improved
- Minimally improved
- No change
- Minimally worse
- Much worse
- Very much worse

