4.6 PHARMACOKINETIC AND PHARMACODYNAMIC ANALYSES

Several candidate PD biomarkers have been identified (e.g., FeNO, blood eosinophils, serum sST2, serum IL-5, plasma LIGHT, and serum amphiregulin) and will be measured to assess the effect of MSTT1041A on these biomarkers. Descriptive summaries of the

PD biomarker values at each visit, as well as changes from the randomization visit (absolute or percent change as appropriate), will be summarized by treatment arm.

The analyses of all PD endpoints will be based on the safety-evaluable population (see Section 4.1.2).

Serum MSTT1041A concentrations are measured at the following timepoints during the double-blind treatment period: Weeks 2, 6, 10, 14, 26, 38, 50, 54, and 70 (Predose, $C_{min,Wk4}$, $C_{min,Wk8}$, $C_{min,Wk12}$, $C_{min,Wk24}$, $C_{min,Wk36}$, $C_{min,Wk48}$, $C_{min,Wk52}$, follow-up concentration). The difference in the weeks for the concentration and the visit week is due to fact that study drug is given on Week 2 of the study, which is the start of the double-blind treatment period. In a subset of patients (approximately 20 per group), additional PK samples will be collected following first dose and at Week 26 for characterization of absorption and accumulation of MSTT1041A following SC administration. These concentrations will be tabulated and summarized using descriptive statistics (mean, standard deviation, coefficient of variation, median, minimum, and maximum) by treatment group and timepoint based on the safety-evaluable population (see Section 4.1.2). While treatment groups will be defined according to the actual treatment received, a review of dosing information including dosing errors, if any, and of the PK data for patients with unusual dosing patterns will be conducted to assess for any potential impact on the results.

Additional PK analyses of the double-blind treatment period data may be conducted as appropriate. Population PK modeling may be performed to characterize inter-individual variability, which may be reported separately from the clinical study report. Exploratory exposure-response analyses will be performed as appropriate, and may be reported separately from the clinical study report.

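### FeNO is read at the site after randomisation and may inform the CGIC, and no masking of FeNO or eosinophils is described: the CGIC is open to contamination by a drug-activity marker, and the primary endpoint to an indirect, unquantified route to bias

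*Protocol*

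**What the plan says.** **The rating.** Protocol 4.5.6.4 describes the CGIC as a single-item clinician rating of change in asthma symptoms, completed at Weeks 26 and 54. The item in Appendix 8 reads "How would you rate the change in the subject's asthma symptoms since they started taking the study drug". On order, Protocol 4.5.6 states "Clinicians will complete the questionnaire after they have examined patients and performed other study-related health assessments". Footnote h of Appendix 1 adds that the clinician evaluates supporting data first, "which may include, but are not limited to, FEV₁, FeNO, and medical records". SAP 4.5.3 compares the proportion rated in the top two improvement categories at Week 54 between each active arm and placebo by logistic regression.

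**FeNO.** Protocol 4.5.13 states "Standard nitric oxide machines will be provided to the site and should be used for all study-related FeNO measurements". After randomisation, Appendix 1 schedules FeNO at Weeks 4, 6, 14, 26, 38 and 54 and at unscheduled visits.

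**Eosinophils.** The differential count belongs to haematology, which goes to central laboratories (Protocol 4.5.14) and is scheduled at every visit from Week 4 to Week 54. Protocol 5.3.5.5 states "It is the investigator's responsibility to review all laboratory findings".

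**Role of the markers.** Protocol 6.8 states "PD biomarkers (e.g., FeNO) will be assessed to determine pharmacological activity and mechanism of action of MSTT1041A". SAP 4.6 begins its list with "Several candidate PD biomarkers have been identified (e.g., FeNO, blood eosinophils".

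**Blinding.** Protocol 4.2 keeps patients, sites, CRO and sponsor agents blind to assignment. The only laboratory matter it addresses is exclusion of placebo PK samples at the bioanalytical laboratories. SAP 3.1 covers randomisation and kit assignment. Neither mentions FeNO or the differential.

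**The concern.** A double-blind design protects more than the treatment code. If the drug moves a marker, anyone who sees that marker over time has some information about the arm. Here the plan itself expects FeNO and eosinophils to show drug activity.

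Two things are at stake:

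- **The CGIC.** A rating meant to capture symptoms can partly reflect FeNO. An arm difference could then arise because the drug lowers FeNO and raters give credit for that, with no difference in symptoms.
- **The primary endpoint.** A protocol-defined exacerbation requires systemic corticosteroid treatment in one of the listed forms (Protocol 6.4.1), which is a clinician's decision. Patients with exacerbation symptoms are asked to attend an unscheduled visit, where FeNO is scheduled. The marker can therefore be read at the visit where treatment may be decided. The sensitivity analyses in SAP 4.5.4 cover model choice and missing data, not differential treatment or recording of events.

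**Working it through.** The plan gives no figure to reproduce: no drug effect on FeNO or eosinophils and no expected CGIC responder rate. The main check is a comparison of the texts; the arithmetic only gives scale under assumptions.

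**1. What is stated and what is inferred**

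- Stated: FeNO is measured at the site after randomisation, and footnote h admits it as a CGIC input. A value offered to the rater cannot also be presumed masked.
- Stated: sites hold reference FeNO values, because change from screening to the randomisation visit is an exclusion criterion (Protocol 4.1.2.2).
- Inferred: sites see eosinophil counts. This follows from the duty to review all laboratory findings and from silence on masking. No text says the central laboratory reports the differential to sites.
- Contrast: patient-reported questionnaires come before disease-status information and other visit procedures (Protocol 4.5.6). The CGIC comes after.

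**2. CGIC, illustration**

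Assume no true effect on symptoms, a placebo responder rate p of 30–50%, and a shift s in the active arm caused by knowledge of the marker. Take n = 125 per arm, or 106 after the 15% dropout in Protocol 6.1 (125 × 0.85). With p̄ = p + s/2:

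- SE0 = √[2p̄(1 − p̄)/n]
- SE1 = √{[p(1 − p) + (p + s)(1 − p − s)]/n}
- nominal false-positive rate ≈ Φ[(s − 1.96·SE0)/SE1]

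Example: n = 125, p = 0.40, s = 0.10. SE0 = √(2 × 0.45 × 0.55/125) = 0.0629. SE1 = √[(0.24 + 0.25)/125] = 0.0626. Φ[(0.10 − 0.1233)/0.0626] = Φ(−0.37) = 35.5%.

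Over the assumed ranges:

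| Shift in responder rate | Nominal false-positive rate |
|---|---|
| 5 points | 11–13% |
| 10 points | 31–38% |
| 15 points | 59–69% |

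**3. Primary endpoint, illustration**

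Inputs: placebo rate 0.63 per year and 125 per arm (Protocol 6.1 and 4.1). Mean follow-up is taken as 1 − 0.15/2 = 0.925 year, assuming dropouts leave halfway on average. Expected placebo events E = 0.63 × 125 × 0.925 = 72.8. The active arm is truly inactive, but a net fraction b of its events is not steroid-treated or not recorded. With dispersion φ:

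- z = −ln(1 − b)/√{φ[1/E + 1/(E(1 − b))]}
- chance of a false benefit = 1 − Φ(1.96 − z)

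Example: b = 0.10, φ = 1. z = 0.1054/√(0.01373 + 0.01525) = 0.619, and 1 − Φ(1.341) = 9.0%.

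| Net suppression b | φ = 1 | φ = 1.5 | φ = 2 |
|---|---|---|---|
| 0 | 2.5% | 2.5% | 2.5% |
| 5% | 4.9% | 4.4% | 4.1% |
| 10% | 9.0% | 7.3% | 6.4% |
| 15% | 15.4% | 11.7% | 9.8% |

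SAP 2.2 assumes no over-dispersion for the overall power statement, but SAP 4.5.1 estimates the dispersion. The φ = 1 column is therefore the upper end.

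**4. What net suppression would require**

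If a marker's change differs by d standard deviations between active and placebo, the best 1:1 guess of the arm is right with probability a = Φ(d/2): 54% at d = 0.2, 60% at 0.5, 66% at 0.8 and 69% at 1.0. If sites suppress a fraction f of events in patients they believe are on active drug, placebo patients guessed wrongly lose events too. Setting (1 − a·f)/[1 − (1 − a)f] = 1 − b gives f = b/[a − (1 − b)(1 − a)].

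- d = 0.5 (a = 0.599): net 5%, 10% and 15% require f ≈ 23%, 42% and 58%.
- d = 0.2 (a = 0.540): they require f ≈ 49%, 80% and more than 100%; the last is impossible.

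**The case against.** The strongest case on the other side has several parts, and much of it limits the point.

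- **Footnote h is permissive.** A reader might infer that raters are instructed to use FeNO. They are not; they may use it. The exposure remains, because use will vary by rater and nothing prevents it.
- **Site sight of eosinophils is not stated.** A laboratory manual outside these documents could mask the differential, and Protocol 5.3.5.5 concerns classifying abnormalities as adverse events. Protocol 8.4 generally withholds exploratory biomarker data from investigators, but gives complexity and exploratory nature as the reason, and footnote h shows it does not keep FeNO from the rater. For eosinophils the objection stands: the defect is an unstated rule.
- **The CGIC is exploratory** and outside type I error control (SAP 4.5). This stands and limits the consequence.
- **A reader might infer that the blind is broken.** The documents do not support this. They give no marker effect; Protocol 4.5.13 notes that FeNO also falls with ICS treatment, so a fall is not specific to study drug; and about 95 of 125 patients per arm are planned to be eosinophil-low.
- **The primary-endpoint route is indirect.** A false benefit by this route needs a drug that moves the marker but not exacerbations. Events also require documented steroid treatment, sometimes by hospital or emergency staff who need not know study FeNO values. Section 4 of the working shows that weak marker effects demand implausibly heavy suppression.

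**Conclusion.** The concern holds in a limited form. FeNO is read at the site after randomisation, masking of FeNO or eosinophils is described nowhere, and footnote h lets FeNO inform a symptom rating that is compared by arm. That leaves the exploratory CGIC open to contamination by one of the plan's own pharmacodynamic markers.

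For the primary endpoint, the route to bias is indirect and its size cannot be derived from the documents. The range of about 4.1–4.9%, 6.4–9.0% and 9.8–15.4% for 5%, 10% and 15% net suppression (dispersion 2 to 1) is illustrative only. It rests on an assumed net suppression, an inactive drug that nonetheless moves a marker, and 0.925 year of mean follow-up. The CGIC shifts are equally assumed. A reader should not conclude that sites are unblinded, that they certainly see eosinophil counts, or that the primary result is biased by a known amount.

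Confidence is high on the FeNO and CGIC text, moderate on eosinophils, and low on any magnitude.

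**What to change.** 1. **CGIC.** Delete FeNO from the inputs in footnote h. Alternatively, have the CGIC completed before FeNO is measured, or by a rater without FeNO and eosinophil results.
2. **Eosinophils.** State in Protocol 4.2 and 4.5.14 that post-randomisation eosinophil results are not reported to sites or blinded sponsor staff. Neutrophil counts and other safety haematology should stay visible: infection is a listed potential risk (Protocol 5.1.1.4) and the absolute neutrophil count is a graded parameter (SAP 4.7.3). The report layout should not let the eosinophil count be recovered by subtraction.
3. **FeNO.** Keep post-randomisation readings from the CGIC rater and treating clinician where the device or staffing already allows. Nothing in the documents shows that the machines can hide a reading, and sites need the screening and randomisation-visit values for eligibility.
4. **Alerts.** Name a timely route for safety alerts that is consistent with Protocol 4.2. The iDMC is unsuitable: its members have no direct contact with site personnel, and it meets about every 3 months.
5. **Reporting.** Give any false-positive figures only as an illustration under assumed net suppression, with over-dispersed values alongside.

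**Cost.** One footnote edit, a change to central laboratory reporting, and some staffing or visit-order arrangements. Sites lose routine sight of eosinophils and the CGIC rater loses FeNO. SAP 2.2 records 502 patients already randomised, so a late change reaches only remaining visits. For ratings already made, the report should say that raters may have known FeNO.

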Appendix 1 Schedule of Activities (cont.)

- ^j Perform a limited, symptom-directed examination at specified timepoints or as clinically indicated. Record new or worsened clinically significant abnormalities on the Adverse Event eCRF.
- ^k Includes respiratory rate, pulse rate, and systolic and diastolic blood pressure while the patient is *ideally* in a seated position, and temperature. Record abnormalities observed prior to dosing at Visit 2 on the General Medical History and Baseline Conditions eCRF. At subsequent visits, record new or worsened clinically significant abnormalities on the Adverse Event eCRF.
- ^l If mean QTcF is >500 ms and/or >60 ms longer than the baseline value, a PK sample will be obtained (if the visit does not already include a scheduled PK sample), see Section 4.5.9. All ECGs are to be obtained prior to other procedures scheduled at that same time (e.g., blood draws). Circumstances that may induce changes in heart rate, including environmental distractions (e.g., television, radio, conversation) should be avoided during the pre-ECG resting period and during ECG recording.
- ^m Patients will use an electronic diary ("eDiary") to record assessments twice a day: in the morning, diary items are asthma symptoms experienced during the night (Asthma Daily Symptom Diary - nighttime), nighttime awakenings, and short-acting rescue medication use, and a single item assessment of overnight symptom severity (PGIS). In the evening, daytime symptom severity (Asthma Daily Symptom Diary - ADSD daytime symptoms), short-acting rescue medication use, and a single-item assessment of daytime symptom severity. Most daily diary items will be completed everyday through Week 54. A single-item compliance with daily controller medication will also be included in the evening diary.
- ⁿ On the days of study visits, if the patient had not performed the morning PEFr measurement before arrival at the clinic, the PEFr should be measured at the clinic.
- ^o A patient's visit must be rescheduled if the patient has used a bronchodilator within the time window defined in Section 4.5.12.1. To accommodate the rescheduled visit, the usual visit window during the treatment period may be extended to ± 4 days for Week 4 or ± 6 days for Weeks 6–54.
- ^p Patients who are not eligible for randomization into the double-blind treatment should be discontinued from the study, and they are not eligible for re-screening. In addition, these patients should be informed that the first dose given at Visit 2 was a placebo and, therefore, there is no additional requirement for follow-up visits.
- ^q Patients who meet all eligibility requirements at screening with the exception of morning pre-bronchodilator FEV₁ of 40%-80% or post-bronchodilator reversibility of FEV₁ of $\geq 12\%$ and ≥ 150 mL are allowed additional attempt(s) to meet the reversibility criteria within the screening or run-in period as described in Section 4.5.2.
- ^r Please refer to Section 4.5.13 for FeNO procedure restrictions.
- ^s Patients with a positive PPD (without a history of Bacillus Calmette-Guérin vaccination) or a positive or indeterminate QFT will require a chest X-ray to review for evidence of active TB, including posteroanterior and lateral views, unless a chest X-ray has been performed within 3 months prior to screening and the report is available for review. A chest CT scan may substitute for a chest X-ray. Chest X-rays should only be performed if patients first meet all other study inclusion criteria.
- ^t All women of childbearing potential will have a serum pregnancy test at screening. Urine pregnancy tests will be performed at specified subsequent visits. If a urine pregnancy test is positive, it must be confirmed by a serum pregnancy test.

Appendix 1 Schedule of Activities (cont.)

- ^u Hematology includes WBC count, RBC count, RBC morphology, hemoglobin, hematocrit, platelet count, ANC, differential count (neutrophils, eosinophils, basophils, monocytes, lymphocytes, other cells).
- ^v Chemistry panel (serum or plasma) includes sodium, potassium, chloride, bicarbonate, glucose, BUN or urea, creatinine, magnesium, total protein, albumin, phosphorus, calcium, total and direct bilirubin, alkaline phosphatase, ALT, AST, uric acid, LDH.
- ^w Lipid panel includes cholesterol, LDL cholesterol, HDL cholesterol, triglycerides.
- ^x If patient has not fasted for 8 hours, patient must return to site for fasting blood draw. Patients will be given 2 weeks to return for a fasting blood draw.
- ^y Includes hepatitis B surface antibody, hepatitis B surface antigen, total hepatitis B core antibody, and hepatitis C virus antibody.
- ^z Measurement of HCV RNA with use of a quantitative PCR assay is only required when the patient was tested positive for HCV antibody at screening and has a known history of HCV antibody positivity with past documentation of undetectable HCV RNA, either with or without history of anti-viral treatment. Patients with newly diagnosed HCV antibody positivity are not eligible for this study and, therefore, do not require measurement of HCV RNA.
- ^{aa} For patients with a HbsAg negative, HbsAb positive, and HbcAb positive test result at screening only, as described in Section 4.1.2.1. Patients with a HBV DNA test value ≥ 20 IU/mL at screening are not eligible. Patients with a HBV DNA test value < 20 IU/mL at screening must undergo re-testing of HBV DNA at Week 14 and Week 38. If the HBV DNA test value at Week 14 and Week 38 is ≥ 20 IU/mL, the medical monitor should be notified.
- ^{bb} Urinalysis includes pH, specific gravity, glucose, protein, ketones, blood, RBCs, WBCs, epithelial cells, bacteria, bilirubin, and leukocyte esterase.
- ^{cc} PK samples to be collected prior to study drug administration.
- ^{dd} Patients will be supplied with urine collection cups to allow for urine sample collection at home prior to coming to the clinic for an unscheduled visit. If the patient did not bring in a urine sample collected at home, the patient will be asked to provide the urine sample at the visit.
- ^{ee} If the DNA is not collected at the randomization visit for any reason, it may be collected at any later timepoint.
- ^{ff} Patients must provide consent to participate. Not applicable for a site that has not been granted approval for RBR sampling. If the DNA is not collected at the randomization visit for any reason, it may be collected at any later timepoint.
- ^{gg} All patients will be held for observation for at least 2 hours after the single-blind placebo dose and after the first five double-blind doses. Dosing on subsequent dosing days should include a minimum length of observation time of 15 minutes, and longer in the event of an injection site reaction, approximately 60 minutes or other, as determined by the investigator.
- ^{hh} Patients will receive MSTT1041A 70 mg, 210 mg, or 490 mg or placebo, administered as four SC injections (one in each quadrant of the abdomen) every 28 ($\pm N$) days (Q4W). More than *one dose* should not be administered within any 21-day period. If the dosing window is missed, that dose will not be administered and the next dose will be administered at the next scheduled dosing date.
- ⁱⁱ Asthma medications used by the patient from 12 months prior to screening through the end-of-study visit should be recorded on the appropriate eCRF. Other medications (e.g., prescription drugs, over-the-counter drugs, vaccines, herbal or homeopathic remedies, nutritional supplements) used by the patient within 3 month prior to screening through the end-of-study visit should be recorded on the Concomitant Medications eCRF.

